Adults with non-progressive ABI sustained in adulthood will be recruited primarily from the Community Treatment Centre for Brain Injury (CTCBI), the main service for community based cognitive rehabilitation in Glasgow. Participants will also be recruited from other NHS services within Scotland.

Inclusion Criteria

- Only those able to give informed consent and able to comply with the training protocol will be included.
- ≥ 6 months post-ABI at time of recruitment (expression of interest to participate either verbally or in writing)
- Adults over the age of 18.
- English language fluency (speaking)
- a combination of self/relative/friend/carer reports of everyday organisation/memory problems

Exclusion Criteria

- Individuals with contra-indications to MRI (e.g. heart pacemaker)
- Comorbid progressive neurological disorder or neurodegenerative condition (e.g. dementia)
- Major psychiatric disorder considered likely to prevent engagement in the intervention programme (pre-ABI history of mood disorder or stable antidepressant medication will not lead to exclusion)
- History of major substance abuse problems if the clinical and research team think it is likely to prevent engagement in and/or interfere with the intervention programme. There will be a degree of flexibility on this and the clinical team will be consulted on an individual basis when deemed necessary.
- Unable to give informed consent
- Unable to cooperate with the study protocol (e.g. severe impairment of hearing, vision or language)

These criteria are necessary in order that the outcome measures can be administered validly, and to increase the likelihood that any neuropsychological impairment present is due to ABI rather than any other pre-existing disorder.

COVID-19 mitigating circumstances regarding inclusion/exclusion criteria

Even though collecting neuroimaging data remains one of the main components of this research project, we understand there may be some participants who feel uncomfortable with travelling and/or coming in contact with others during the COVID-19 crisis. Therefore, individuals with MRI contraindications can still be included to take part in the behavioural intervention sessions without completing the fMRI sessions as an exception; nevertheless the focus still remains on recruiting participants suitable for brain imaging.

iii. Procedure

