The study will entail 12 visits overall. Details regarding the components and content of each visit are described in the following subsections of the protocol (please also refer to Table 1 below for a brief summary). No changes in routine care will take place while participating in the study.

Table 1: Research procedure

Visit Number	Visit 0	Visit 1	Visit 2	Visit 3	Visit 4	Visit 5	Visit 6	Visit 7	Visit 8	Visit 9	Visit 10	Visit 11	Visit 12
Type of Visit	Screening	Baseline T0	fMRI Time 1 (T1)	Treat Wk 1	Treat Wk 2	Treat Wk 3	Treat Wk 4	Treat Wk 5	Treat Wk 6	Treat Wk 7	Treat Wk 8	fMRI Time 2 (T2)	Immediate Follow-up T3
Time since last visit			≤ 1 wk from Visit 1	≤ 1 wk from visit 2	1 wk from visit 3	1 wk from visit 4	1 wk from visit 5	1 wk from visit 6	1 wk from visit 7	1 wk from visit 8	1 wk from visit 9	≤ 1 wk from visit 10	≤ 1 wk from visit 10
fMRI session			x									x	
GMT Introductory session		x											
GMT session				x	x	x	x	x	x	x	x		
WMU AT session				x	x	x	x	x	x	x	x		
WMU NA session				x	x	x	x	x	x	x	x		
Neuropsychology Assessment		x											x
Functional Assessment		x											x

Post- Interventio n Participant Feedback													X
--	--	--	--	--	--	--	--	--	--	--	--	--	---

Wk: week, T: Time, GMT: Goal Management Training, WMU: Working Memory Updating, AT: Adaptive, NA: Non Adaptive, fMRI: functional Magnetic Resonance Imaging.

iv. *Recruitment*

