The training consists of computerised working memory updating tasks in which trial accuracy and response time are recorded. All 8 WMU interventions will be delivered by the PhD researcher on a group basis (group size N = 2 – 6). Two computerised WMU tasks will be trained based on the study conducted by [name] on healthy adults (Flegal et al., 2019). These tasks will be delivered via two modalities: (1) a visuospatial WMU task, i.e. Matrix Updating (MU) and (2) a verbal WMU task, i.e. Keep Track (KT). MU requires updating the location of multiple dots within a 4 x 4 matrix (Chen and Li, 2007) while KT requires updating the identity of the most recently studied words in multiple semantic categories (Yntema, 1963). For both training tasks, level of difficulty can be modulated by increasing or decreasing the update level, i.e., the number of updates on each trial. For AT participants, difficulty of the training tasks is progressively increased in response to task performance, in order to adaptively increase environmental demands. For NA participants, however, task difficulty is fixed at a relatively low level across all sessions. Training of the MU task lasts between 25-30 minutes while the KT training lasts between 20-25 minutes. The WMU training sessions will last between one hour to one hour and fifteen minutes taking into consideration time to provide instructions and practice.

ix. Post-intervention Feedback

After the end of the intervention all participants will have the opportunity to rate the perceived usefulness and experience of the interventions including any adverse effects using Likert scales (for further details please see the feedback form). This information will be used to guide the possible development of a future full-scale trial. This will be carried together with the immediate follow-up session after the end of the intervention (i.e. visit 12) by the PhD researcher.

x. Outline of Study Visits

Visit 1: Baseline Neuropsychological and Functional Assessment and Introductory GMT session

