At both T1 and T2 the task runs will be followed by a T1-weighted sequence to obtain high-resolution anatomical images. In conducting fMRI data analysis the functional images will be spatially realigned using a six-parameter rigid body transformation and coregistered to their T1-weighted anatomical image. In total, visits 2 and 11 will take around two hours to complete, i.e. thirty minutes for the safety procedure prior to the scan and another one hour and a half for the scanning procedure itself. Comparisons in scanned task performance between T1 and T2 will allow us to examine how much benefit is gained due to the training intervention and if there is evidence of generalisation to other untrained tasks. In addition, we will examine neural changes in terms of task-related brain activity.

The procedure and tasks will be identical at T1 and T2, with the exception of three structural imaging sequences acquired only at T1, in addition to the T1-weighted anatomical image, for the purposes of a comprehensive, accurate and detailed neuroradiologist report (please see sections 6 and 7 below). These additional sequences are: 1. Axial T2-weighted, 2. Axial T2-weighted fluid attenuation recovery (FLAIR), and 3. A haemosiderin sensitive sequence.

For both fMRI sessions, the participants will spend no more than one hour inside the scanner.

Visits 3- 10: GMT+WMU Intervention sessions

There will be 8 weeks of a combined GMT and WMU intervention. Each GMT session will be two hours long while the WMU session will last between one hour and one hour and fifteen minutes. There will be a break between the training sessions allowing participants to have a rest and relax lasting between thirty minutes to an hour. The intervention visits will be conducted either at the Psychology department, University of Glasgow or at the CTCBI. Both GMT and WMU sessions will be administered by the PhD researcher undertaking the project. These will be conducted weekly on a group level at the same day; that means each intervention visit will last approximately three hours and forty-five minutes to four hours including the break in between. If attending both intervention sessions at the same day is not feasible for some participants, due to reasons such as getting easily fatigued or not being able to commit this long on the same day, the following guidelines will be implemented:

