1. The option of coming for the two interventions separately within the same week will be offered, i.e. arranging the GMT and WMU interventions at two different times.
2. The option of conducting the WMU intervention in one's own time at home will be offered after the PhD researcher makes sure the necessary requirements are in place, i.e. the participant has a laptop at home to perform the training tasks, they have fully understood the tasks and are practicing according to the guidelines. Under these conditions, task performance will be monitored from encrypted anonymised data files (logging trial accuracy and response time) transmitted to the PhD researcher via e-mail at the end of each at-home training session.

Visit 12: T3, Immediate follow-up: neuropsychological and functional assessments

All standardised measures that were administered at baseline (Visit 1) will be re-administered after the end of the intervention (please see table 1) by the PhD researcher. An acceptable period between the end of the intervention and neuropsychology assessment will be within three weeks. In addition, a feedback form will be given to the participants to rate the perceived usefulness and experience of the interventions. This final visit will last around one and a half hours.

The PhD researcher will have access to supervision and will be given advice regarding what steps to take, including sharing relevant information, if they become concerned about the welfare of the participant at any stage during the study.

xi. *COVID-19 mitigation plan- Online option for study visits 1, 3-10 and 12.*

An online alternative will be offered to run the study visits remotely in order to minimise the risk of infection due to COVID-19. As a result, no unnecessary travelling nor physical group sessions will be taking place. In more detail:

- *Neuropsychology assessment - Visits 1 and 12*

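### Adverse effects are asked about only once, by Likert self-report at Visit 12, so early or transient effects are likely to be under-reported

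*Combined protocol and SAP*

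**What the plan says.** Section 4.ix (Post-intervention Feedback) has participants "rate the perceived usefulness and experience of the interventions including any adverse effects using Likert scales". The form is completed at the "immediate follow-up session after the end of the intervention (i.e. visit 12) by the PhD researcher", and Table 1 marks participant feedback at Visit 12 only. The form itself is cited but is not part of the documents.

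The inclusion criteria in section 4.ii call for "a combination of self/relative/friend/carer reports of everyday organisation/memory problems". Section 4.vii separately offers appointment reminders, because some participants may have trouble remembering.

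On timing, section 4.x states: "There will be 8 weeks of a combined GMT and WMU intervention". Table 1 places Visit 12 at "≤ 1 wk from visit 10". The Visit 12 text in section 4.x says instead: "An acceptable period between the end of the intervention and neuropsychology assessment will be within three weeks".

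The only other text bearing on safety during training is a sentence in section 4.x. It gives the PhD researcher supervision and advice if a participant's welfare causes concern. Section 4.x also foresees that some people may not manage both sessions in one day, "due to reasons such as getting easily fatigued", and offers them separate sessions or home WMU training.

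The Statistical methods section lists recruitment, adherence and retention as percentages with 95% CI. It contains no summary of adverse effects.

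**The concern.** Acceptability is a primary outcome (section 3.i), and section 4.ix says the feedback is to inform a possible full-scale trial. If unwanted effects are asked about only after training has ended, a headache, fatigue or distress in the first weeks that has since passed may be forgotten or discounted. People included for organisation or memory problems are more exposed to this than most. The error runs mainly one way: forgotten effects make the intervention look better tolerated.

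Nor does the plan provide anything else from which a count could be made. There is no question at each session, no diary, no log and no definition of an adverse effect. A confidence interval around the Visit 12 figure would reflect sampling error only and would not show the loss.

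**Working it through.** The plan states no adverse-effect rate, recall rate or safety target, so there is no figure of its own to reproduce. What can be checked is the recall interval and, by assumption only, what imperfect recall would do.

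**Recall interval.** Inputs: eight weekly combined sessions at Visits 3 to 10 (Table 1), and a gap from Visit 10 to Visit 12 of at most 1 week (Table 1) or at most 3 weeks (section 4.x).

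- First to last combined session: 7 intervals × 1 week = 7 weeks.
- From the first combined session to the form: 7 to 7 + 1 = 8 weeks by Table 1; 7 to 7 + 3 = 10 weeks by section 4.x.
- From the last session: 0 to 1 week, or 0 to 3 weeks.
- Average over the eight sessions: (0 + 1 + … + 7)/8 = 28/8 = 3.5 weeks, plus the gap. This gives 3.5 to 4.5 weeks by Table 1, or 3.5 to 6.5 weeks by section 4.x.
- GMT module 1 is given at Visit 1, up to 1 + 1 = 2 weeks before Visit 3. Counted from there, the maximum is 10 weeks (Table 1) or 12 weeks (section 4.x).

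So 8 or 10 weeks is the longest interval for the combined sessions and applies to the first of them. The average is roughly half to two-thirds of that.

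**Illustration of under-recall.** Every rate here is an assumption. Let *p* be the true proportion with an effect and *s* the proportion of those who report it. Assume all 32 participants (16 per arm) complete the form and respond independently. The expected number reporting is 32*ps*. The chance of at least one report in an arm is 1 − (1 − *ps*)^16.

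| *p* | *s* | Expected reports, 32 people | At least one report in an arm of 16 |
|---|---|---|---|
| 10% | 100% | 3.2 | 1 − 0.90^16 = 81% |
| 10% | 80% | 2.6 | 1 − 0.92^16 = 74% |
| 10% | 50% | 1.6 | 1 − 0.95^16 = 56% |
| 25% | 100% | 8.0 | 1 − 0.75^16 = 99% |
| 25% | 80% | 6.4 | 1 − 0.80^16 = 97% |
| 25% | 50% | 4.0 | 1 − 0.875^16 = 88% |

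With mild under-recall the loss is small; with 50% recall it halves the expected count. The documents do not say where in this range the study lies.

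**The case against.** The best reply is that this is a small feasibility study of behavioural training with a great deal of contact. GMT is given weekly in groups of 2 to 6 by the researcher and a second team member, homework is reviewed at the next session, and radiography staff are present at the scans. Effects can be mentioned at any of these contacts, and the welfare provision and fatigue options allow a response. This stands as an answer on participant care. It does not answer the measurement point, because none of these contacts asks a standard question or is said to produce a record that could be counted.

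A second reply is that the form has not been seen. This also stands, and it rules out several stronger readings that a reader might infer:

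- *Recall is unaided, the component cannot be identified, and the scans are not covered.* The form may contain prompts, free text or separate ratings for GMT and WMU. The documents do not settle it.
- *Nobody can act on an early effect.* The welfare sentence and the fatigue options say otherwise. Not being asked is different from being unable to respond.
- *Those training at home are the least observed.* Home practice replaces only the WMU part, and GMT contact continues. Under the COVID-19 option in section 4.xi, WMU is remote in any case.
- *A difference between arms is hidden.* Both arms have the same form at the same time. If burden grows with adaptive difficulty, it is greatest in the late sessions, nearest to Visit 12.

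Third, the inclusion criterion covers organisation or memory problems, so not every participant need have poor memory.

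**Conclusion.** The point holds in a limited form. The documents show one elicitation of adverse effects, at Visit 12, up to 8 weeks (Table 1) or up to 10 weeks (section 4.x) after the first combined session, and no planned summary. Early or transient effects are therefore likely to be under-reported among those who complete the form, in the direction that favours acceptability.

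It would be going too far to say that effects will be under-counted, or that they must typically be recalled over 8 to 10 weeks. The first needs an effect rate and a recall rate that the documents do not give; the second takes the maximum for the typical interval. The judgement rests on two things: the text of section 4.ix and Table 1 being the whole of the elicitation, and the reasonable assumption that recall in this population is imperfect.

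This is a cheap improvement worth making. It does not undermine the design. The disagreement between the two Visit 12 windows stands on its own and must be reconciled.

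**What to change.** 1. At Visits 2, 3-10, 11 and 12, put one identically worded question to each participant individually, for example: *Since we last met, have you had any unwanted effect that you link to the sessions, the home practice or the scan?* In group sessions use a short written slip, so that answers are private and do not prompt others. For home or remote WMU, return the answer with the data file or by e-mail.
2. Log the date, the component (GMT, WMU or scan) and any action taken.
3. Add to Statistical methods the number and percentage of participants with any logged effect, by arm and overall, with 95% CI. The intervals will be wide: even no reports among 16 gives a one-sided 95% upper limit of 1 − 0.05^(1/16) = 17%.
4. Keep the Visit 12 Likert form for usefulness and experience.
5. Reconcile the Visit 12 window between Table 1 and section 4.x.

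The cost is a protocol paragraph, a simple log and a few minutes per group session, with no new visits. Regular prompting will raise the number of minor effects reported, which should be remembered when the rate is compared with studies that asked only once.

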Full details of baseline assessment is given in section V: *Baseline neuropsychological and functional assessments*. Following completion of the assessments, the PhD researcher will then proceed with the introductory GMT session where the idea behind the intervention as well as its usefulness in people with ABI will be presented. Emphasis will be given on the importance of having goals in everyday life and a few key concepts central to GMT will be mentioned. In addition, the PhD researcher will discuss the expectations clients should have from this intervention, i.e. learn strategies, practice relaxation techniques, take control by stopping and thinking about their goals when performing a task. The overall duration of Visit 1 will be around three hours (approximately one to one and half hours for the neuropsychology assessment, half an hour for a break and one hour for the first introductory GMT session).

There is a very small possibility the PhD student might be required to make a few home visits as an exception (assuming the participant has a great difficulty travelling themselves on a day) in order to complete neuropsychological assessments, which carry a potential personal safety risk. To minimise these risks, all home visits will be carried out during office hours and the PhD student will be required to carry mobile phones and to let a member of the research team (or if not possible, a member of staff at their usual place of work) know when and where their appointments are and when they have finished. Hence, the University of Glasgow lone

study policy will be followed. Please follow this link for further information https://www.gla.ac.uk/media/Media_500540_smxx.pdf

Visits 2 and 11: Time 1 and Time 2 fMRI sessions

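### The only participant rating described is collected at Visit 12, and no route is described for people who leave the study before that visit or miss it (minor, cheap to improve)

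*Combined protocol and SAP*

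**What the plan says.** Section 3.i lists acceptability with feasibility and fidelity as the primary outcomes. Section 4.ix gives all participants the chance to rate the usefulness and experience of the interventions, "including any adverse effects using Likert scales (for further details please see the feedback form"). It fixes the occasion: "This will be carried together with the immediate follow-up session after the end of the intervention (i.e. visit 12) by the PhD researcher". It also gives the purpose: "This information will be used to guide the possible development of a future full-scale trial".

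Two other places agree on timing. Table 1 marks participant feedback at Visit 12 only. The Visit 12 text in section 4.x says that "a feedback form will be given to the participants to rate the perceived usefulness and experience of the interventions"; it does not repeat the mention of adverse effects.

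The Statistical methods section plans percentages with 95% confidence intervals for recruitment, adherence and retention. For cognitive, psychological and functional measures it plans summaries by group and overall. It does not name the feedback ratings or adverse effects.

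The feedback form, consent form and data management plan are separate documents and were not available for this review.

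**The concern.** A person who leaves an intervention study early may have left because of the intervention. The protocol itself foresees burden: intervention visits last close to four hours, and section 4.x makes allowance for people who tire easily or cannot commit that long in one day. If the only rating is taken at the last visit and nobody contacts those who have gone, the ratings describe people who reached that visit. Adverse effects are exposed in the same way, since the form is the only described means of asking participants about them.

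The ratings are meant to inform a full-scale trial, and the Dissemination plan makes further steps conditional on the intervention proving feasible and acceptable. Views not sought when a person leaves may be impossible to recover later.

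**Working it through.** The plan has no figure to reproduce here beyond the allocation: 16 per group × 2 = 32, which agrees with the Sample size section. The check is a reading of the text, followed by an illustration.

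**Who is reached, on the text as written**

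| Participant | Rating collected? | Basis |
|---|---|---|
| Completes sessions, attends Visit 12 | Yes | 4.ix; Visit 12 |
| Stops sessions, still attends Visit 12 (in person or online) | Yes | 4.ix covers all participants; nothing limits the form to completers |
| Leaves the study before Visit 12, or misses it | No route described | No exit form, call or visit in 4.ix, Table 1 or the Visit 12 text |

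The gap is the third row only. Retention would show how many people are in it, but not their ratings or adverse effects.

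**Illustration of size**

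Inputs from the documents: N = 32 planned. Assumptions, because the documents give none of these: m = 6 forms missing; a rating can be classed as favourable or not; 21 or 23 of the 26 returned forms are favourable; all 32 started the group sessions.

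With k favourable forms returned, the share among all N lies between k/N (every missing form unfavourable) and (k + m)/N (every missing form favourable). The width is m/N.

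- k = 21: returned forms 21/26 = 81%. Range 21/32 = 66% to 27/32 = 84%.
- k = 23: returned forms 23/26 = 88%. Range 23/32 = 72% to 29/32 = 91%.
- Width in both cases: 6/32 = 19 percentage points.
- If 3 of the 6 forms were recovered, the width would be 3/32 = 9 points.

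For scale, the Wilson 95% intervals for the returned forms are 62-92% (21/26) and 71-96% (23/26). In both examples sampling error is wider than the range from missing forms.

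**Adverse effects, same method**

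Assume 3 of the 26 returned forms report one, 3/26 = 12%. Among all 32 the share could be 3/32 = 9% to 9/32 = 28%.

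**The case against.** The strongest reply is that the plan already makes a missed form unlikely. Section 4.ix addresses all participants. Section 4.xi provides an "Online option for study visits 1, 3-10 and 12". For timing, "An acceptable period between the end of the intervention and neuropsychology assessment will be within three weeks". The Visit 1 text says the student "might be required to make a few home visits as an exception" to complete assessments. Welfare concerns can be raised with supervisors at any stage. These points stand as mitigation. None is described as a way of collecting ratings from someone who has left.

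A second reply is that a withdrawal procedure would naturally sit in the consent material. That is possible and cannot be checked here, which is why the fix allows a cross-reference.

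A third is that this is a small feasibility study, not powered for group differences and with no acceptability threshold. That limits the severity, but acceptability is still a primary outcome.

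Some stronger readings are tempting, and the documents do not support them:

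- A reader might infer that everyone who stops training goes unrated. Nothing bars such a person from Visit 12.
- A reader might infer that the form is the acceptability measure. No section says so. Adherence and retention could also be read as behavioural signs of acceptability, though the protocol does not define them that way.
- A reader might infer a number of missing forms beyond which the ratings cannot be trusted. Any such number depends on the assumed favourable rate. With 7 missing, 22/25 favourable puts the worst case (22/32 = 69%) just below the Wilson lower limit of 70%, while 20/25 puts it (20/32 = 62.5%) above the limit of 60.9%. No tipping point is claimed.
- A reader might take the absence of a stated summary or denominator as a fault in itself. Alone, it is only missing detail.

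**Conclusion.** The point holds as a minor, cheap improvement. On the documents available, the only described participant rating is tied to Visit 12, and people who leave the study before it or miss it have no described route to give one. If they are less favourable than attenders, the ratings will look too good; the documents do not show that they would be. The size and direction are unknown. The 66-84% and 72-91% ranges rest wholly on the assumed 6 missing forms and the assumed favourable counts, and show only what could go unseen. No figure in the plan is wrong, and the sample size is unaffected. The conclusion would fall away if the feedback or consent documents already provide for contact after withdrawal.

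**What to change.** **Collection.** In section 4.ix, state that the same form is offered by post, e-mail or phone to every randomised participant who leaves the study or misses Visit 12, unless that person declines contact and subject to the consent terms. If the feedback or consent documents already provide this, cross-refer to them.

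**Reporting.** In the Statistical methods, say that ratings and reported adverse effects will be given by arm and overall, with forms returned shown out of the number actually randomised and out of the number who started the group sessions. Use actual numbers, not the planned 16 and 32. Randomisation follows the baseline assessments and precedes the group sessions, so some people may be randomised and never start. Show them separately, and apply any best-case and worst-case range only to those who started, since a person who never trained cannot rate the training.

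**Cost.** A few sentences of text and one extra contact per leaver; no new visit, instrument or staff. There are two downsides to accept. Answers may be more polite when the form is taken by the researcher who delivered the sessions, and the acceptability figure may come out less favourable.
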